[figure not shown]

17 OCT 2019  
Date

SUMMARY OF CHANGES OF THIS VERSION 2.0) VERSUS PREVIOUS VERSION (1.0)

Version 1.0 of this SAP was not implemented, as the study protocol was amended prior to database lock and final statistical analysis to include 3 additional dose cohorts. Version 2.0 of this SAP has incorporated analysis for dose cohorts 7 (24 mg), 8 (27 mg) and 9 (30 mg). No modifications to analysis plans have been made other than removing analysis of cotinine and 3-OH cotinine, as testing will not be conducted, per the Sponsor.

## 2.2. List of Abbreviations

ADAE	Analysis Data Adverse Events
ADaM	Analysis Data Model
ADEG	Analysis Data Electrocardiogram
ADaMIG	Analysis Data Model Implementation Guide
ADLB	Analysis Data Laboratory
ADPC	Analysis Data Pharmacokinetic Concentrations
ADPP	Analysis Data Pharmacokinetic Parameters
ADSL	Analysis Dataset, Subject-Level
ADVS	Analysis Data Vital Signs
AE	Adverse Event
ALP	Alkaline Phosphatase
ALT	Alanine Aminotransferase
$A_{\text{mean}}$	Arithmetic mean
aPTT	Activated Partial Thromboplastin Time
AST	Aspartate Aminotransferase
ATC	Anatomic Therapeutic Class
BLQ	Below the Limit of Quantification
BMI	Body Mass Index
$C_{\text{max}}$	Maximum Observed Plasma Concentration
CO	Carbon Monoxide
CPK	Creatine Phosphokinase
CR	Clinically Relevant
$Cr_{\text{CL}}$	Creatinine Clearance
CSR	Clinical Study Report
CV%	Coefficient of Variation
DBP	Diastolic Blood Pressure
DSM	Data Safety Monitor
ECG	Electrocardiogram
GGT	Gamma-Glutamyltransferase
GLP	Good Laboratory Practice
$G_{\text{mean}}$	Geometric mean
hCG	Human Chorionic Gonadotropin
HIV	Human Immunodeficiency Virus
INR	International Normalized Ratio
LC-MS/MS	Liquid Chromatography with Tandem Mass Spectrometry
LDH	Lactate Dehydrogenase
LLOQ	Lower Limit of Quantification
MCH	Mean Corpuscular Hemoglobin
MCHC	Mean Corpuscular Hemoglobin Concentration
MCV	Mean Corpuscular Volume
MedDRA	Medical Dictionary for Regulatory Activities
NCR	Not Clinically Relevant
NMR	Nicotine Metabolite Ratio
PI	Principal Investigator
PT	MedDRA Preferred Term
RBC	Red Blood Cell

---

RDW-CV	Coefficient Variation of the Red Cell Distribution Width
SAE	Serious Adverse Event
SAP	Statistical Analysis Plan
SBP	Systolic Blood Pressure
SD	Standard Deviation
SOC	MedDRA System Organ Class
TEAE	Treatment-Emergent Adverse Events
TFLs	Tables, figures and listings
T max	Time of Occurrence of Maximum Observed Plasma Concentration
ULOQ	Upper Limit of Quantification
WBC	White Blood Cell

### 3. INTRODUCTION

This Statistical Analysis Plan (SAP) presents the details of the analysis and presentation of the safety and pharmacokinetic (PK) results for Clinical Study ACH-CYT-08.

The analyses described are based on the Clinical Study Protocol (CSP) version 5.0, dated 07MAY2019 [1].

This SAP will be finalized and approved by the Achieve Life Sciences (Achieve) and [REDACTED]'s representatives prior to the planned database lock and unblinding of study treatment assignment code. Any deviations from this SAP will be described in detail and justified in the Clinical Study Report (CSR). If additional analyses are required to complement the analyses planned in the SAP, they may be performed and will be identified in the Clinical Study Report (CSR).

#### 3.1. Summary of Changes from Protocol or Its Amendments

There are no changes from the protocol or its amendments.

#### 3.2. Reporting and Deliverables

The CSR will be written using the Achieve's template. Tables, Figures and Listings (TFLs) will be prepared as described in the TFL shells within this SAP. In-text Tables and Figures will be included in the main body of the CSR. After review by the Sponsor, the TFLs will be finalized.

Before performing the analysis, all data collected will be integrated into a common repository, using SAS 9.4 (SAS Institute Inc, Cary, NC, USA). Derived analysis datasets will be generated in accordance to CDISC. ADaM compliant datasets will be delivered to the Sponsor.

[figure not shown]
### 4. STUDY OBJECTIVES

#### 4.1. Primary

To assess the tolerability and safety of cytisine as a single oral dose.

#### 4.2. Secondary

To define the  $C_{max}$  levels associated to the occurrence of dose-limiting adverse events.

## 5. STUDY DESIGN OVERVIEW

### 5.1. Study Design

[figure not shown]
This was a single-center, double-blind, randomized, placebo-controlled, single dose-escalation, Phase 1 clinical study conducted in male or female adults who were in good general health and were current daily cigarette smokers, under fasting conditions.

Nine dose levels were pre-planned under version 5.0 of Protocol ACH-CYT-08: 6 mg, 9 mg, 12 mg, 15 mg, 18 mg, 21 mg, 24 mg, 27 mg and 30 mg. The starting dose was 6 mg cytisine (single oral dose) in Cohort 1. The study was escalated up to the cytisine dose of 30 mg in Cohort 9 without showing any of the predefined stopping criteria. Within each dose level, subjects were randomly assigned to receive a single oral dose of cytisine or placebo in a 3:1 ratio (6 cytisine:2 placebo).

Upon completion of a cohort, a safety review was performed by the Principal Investigator (PI) and two independent Data Safety Monitors (DSMs) on unblinded data. The PI and DSMs conjointly decided whether dose escalation into the next cohort was to be allowed.

Table 1 presents an overview of study design.

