### 5.4. Method of Assigning Subjects to Treatments

Using SAS® 9.4, a computer-generated block-wise randomization list adequate for placebo-controlled studies was prepared by the Programming & Biostatistics Department of [REDACTED]. At each cohort, 6 subjects were randomly assigned to receive cytisine and 2 subjects randomized to receive placebo.

Upon confirmation that all eligibility criteria are met on Day 0, subjects were sequentially assigned a randomization number. The randomization number was provided to the unblinded Pharmacist on site and defined the treatment to which subjects were allocated (test or placebo) per the randomization list.

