### 7.2. Acceptance of Data

TFLs may start being programmed prior to, or during, the course of the trial. However, the programming of analysis datasets (ADS) and TFLs will only be finished and quality-controlled after database soft lock and unblinding of the data. Only audited cytisine plasma concentration data released by the Bioanalytical Laboratory will be used

for programming the final pharmacokinetic ADS and TFLs.

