## **8.7. Safety Assessments**

### **8.7.1. Adverse Events**

Clinically significant abnormalities will be reported as AEs. Adverse events will be coded using the MedDRA dictionary version 21.1 or higher. Coding includes system organ class (SOC) and preferred term (PT). The following information recorded or computed is used for the description of the AEs: reported Term; SOC and PT by MedDRA coding; start date, start time, end date and end time; seriousness; severity (intensity); relationship (causality); action taken; outcome. AE duration and time to AE onset will be derived and presented in the subject data listings.

TEAEs will be presented by dose level. TEAEs are defined as AEs not present prior to administration of investigational product, or AEs present before administration of investigational product that worsen after the subject received the investigational product. A separate listing of SAEs will be presented, if applicable. Frequencies of TEAEs will be presented by SOC and PT, by Test product and placebo and overall.

TEAEs of which the relationship to the test drug was classified as ‘possible’, ‘probable’ and ‘definite’ will be regarded as “related”, while TEAEs that are classified as ‘not related’ or ‘unlikely’ will be regarded as “not related”.

Frequencies of TEAEs will also be reported by severity class (Mild, Moderate, or

Severe) and by investigational product and dose, for all causalities and for “related” events.

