### 8.7.2. Laboratory Data

Individual laboratory test data will be listed. A listing of the values outside the pre-specified ranges will be flagged (“H” - high or “L” - low) and classified regarding clinical relevance.

A decision regarding whether a result outside the reference range is of clinical significance or not was made by the clinical investigator and reported and annotated accordingly. Clinically significant abnormalities occurring during the study will be recorded as AEs.

The reference ranges for the site’s laboratory parameters will also be entered in the database and filed in the Investigator site file.

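### Does the PI's unblinded review after each cohort undermine the double-blind label and the tables of related adverse events?

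*SAP*

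**What the plan says.** Section 5.1 opens with "This was a single-center, double-blind, randomized, placebo-controlled, single dose-escalation, Phase 1 clinical study". The same section says that when a cohort was complete "a safety review was performed by the Principal Investigator (PI) and two independent Data Safety Monitors (DSMs) on unblinded data", and that "The PI and DSMs conjointly decided whether dose escalation into the next cohort was to be allowed". It also reports in the past tense that escalation reached 30 mg in Cohort 9. Section 5.4 mentions one other unblinded role: "The randomization number was provided to the unblinded Pharmacist on site".

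Two sections speak of unblinding as a later event. Section 3 has the SAP approved "prior to the planned database lock and unblinding of study treatment assignment code". Section 7.2 says that the analysis datasets and TFLs "will only be finished and quality-controlled after database soft lock and unblinding of the data". Section 12 lists minutes of a blind data review dated 10 October 2019.

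On ratings, Section 8.7.1 splits events into related and not related by the recorded causality class ("TEAEs of which the relationship to the test drug was classified as"). It names neither the rater nor the time of rating. Section 8.7.2 says that the decision on clinical significance of a laboratory result "was made by the clinical investigator and reported and annotated accordingly". Section 7.1 refers data handling to the protocol and the Data Management Plan.

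**The concern.** Read quickly, the SAP describes two different trials. In one, nobody at the site except the pharmacist knows the allocation until the database is locked. In the other, the PI of a single-centre study sees unblinded data cohort by cohort and shares in the escalation decision.

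If the PI also rated causality, severity or clinical relevance, a rating entered or revised after a cohort's review could have been made with the treatment known. These ratings are subjective. They feed Tables G.2, 14.2.1.4 and 14.2.1.6, and safety and tolerability are the primary objective. The SAP has no rule that separates ratings made before a cohort's review from those made after it. Section 7.2 also pairs unblinding with a soft lock, which can normally be reopened. With six cytisine and two placebo subjects per cohort, a few reclassified events would visibly change the related-TEAE percentages.

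**Working it through.** **Inputs.** Nine cohorts and 72 planned subjects (Sections 5.1 and 5.2). Six cytisine and two placebo per cohort (Sections 5.1 and 5.4). Placebo is shown as a single treatment group in summaries (Section 8).

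**The plan's own figure.** 9 × (6 + 2) = 72, which matches Section 5.2. By arm: 9 × 6 = 54 cytisine and 9 × 2 = 18 placebo.

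**How much the PI could have seen.** Reaching Cohort 9 requires eight escalation reviews: 8 × 8 = 64 subjects, and 64/72 = 88.9%. A ninth review, after Cohort 9, would bring this to 72 of 72. The general wording of Section 5.1 suggests a ninth, but only eight follow from the escalation itself. Both counts assume that unblinded data means individual treatment codes, which the SAP does not say.

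**Effect of one reclassified subject on a related-TEAE percentage.**
- One dose group: 1/6 = 16.7 points.
- Pooled placebo: 1/18 = 5.6 points.
- All cytisine: 1/54 = 1.9 points.

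These are the effects of any one-subject change in groups of this size. They give neither a number of changed ratings nor a direction of bias, and the SAP supplies neither.

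**The statements on blinding, side by side.**
1. Within a cohort, Section 5.4 describes allocation through an unblinded pharmacist. Nothing says that anyone who doses or assesses subjects knows the code at that stage.
2. Section 5.1 places the unblinded review after the cohort is complete, so that review need not disturb blinded assessment within the cohort.
3. Section 3 concerns approval of the SAP, and Section 7.2 concerns programming of datasets and outputs. Both read naturally as release of the code to the analysis team.
4. The blind data review minutes (10 October 2019) precede the date of 17 October 2019 that stands ahead of the summary of changes for version 2.0. This order fits an analysis team that was still blind.

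The four steps can be put in one order without conflict.

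**The link from the review to the tables.** For bias to reach the related tables, three things must hold: the unblinded PI assigned the ratings, some ratings were set or changed after the cohort's review, and no procedure prevented or recorded this. Section 8.7.1 does not establish the first. Section 8.7.2 names the clinical investigator, but only for laboratory results. No section reports the second. The third depends on the protocol and Data Management Plan, to which Section 7.1 defers.

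**What does not depend on relatedness.** Tables G.1, 14.2.1.3 and 14.2.1.5 count all TEAEs whatever their cause, and Listing 16.2.5.6 shows each one.

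**The case for a change.** The strongest case for acting is that the reader cannot tell from the SAP who knew what, and when. At a single centre, overlap between the unblinded PI and the raters is plausible. The safety summaries in Section 14.2 are all adverse-event outputs. Laboratory, vital-sign and ECG findings are only listed, and count in those summaries only if judged clinically relevant. For continuous monitoring, Section 8.7.3 provides no listing at all, so in the planned outputs that judgement is the only trace. With no comparisons between cohorts planned unless otherwise indicated, the percentages are the main result.

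What stands is that the SAP does not spell out who was unblinded and when. A sentence in the study report's description of blinding would settle it. That is missing detail rather than an error of analysis.

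The possible remedies do not improve the plan:
- Building the related tables on ratings frozen before each review would drop legitimate later information, such as an ongoing event that worsens or a corrected error. Safety findings could then be understated. At most this would serve as a sensitivity display, if ratings turned out to have changed.
- Naming the all-causality tables as the main ones relabels outputs already planned.
- Requiring a hard lock before code release is an operational preference. Section 7.2 says when programming is finished, not that adverse-event ratings stay open until then.

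**Conclusion.** No change to the plan follows. Double-blind is a loose description of a trial whose PI saw unblinded data after completed cohorts, but it is compatible with blinded conduct within each cohort and with later release of the code for analysis. The exposure that can be established is eight reviews and 64 of 72 planned subjects, and this holds only if individual codes were shown. The 16.7-point and 5.6-point shifts reflect group size and do not demonstrate bias.

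This conclusion rests on two readings. The first is that Sections 3 and 7.2 refer to the analysis team, which fits their context but is not stated. The second is that control of rating changes belongs to the protocol and Data Management Plan, as Section 7.1 indicates. Evidence that causality or severity ratings were altered after a cohort's review would be a reason to list those changes. The SAP contains no such evidence.

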**Figure 1. Study Diagram:**

### 5.2. Number of Subjects

The study protocol defined a sample size of 8 subjects per cohort, which is consistent with standard practice in early-phase clinical trials with similar study objectives.

Considering that 9 cohorts were pre-planned, a total of 72 subjects was estimated for enrollment.

### 5.3. Number of Clinical Sites

This was a single center clinical trial.

### 5.4. Method of Assigning Subjects to Treatments

Using SAS® 9.4, a computer-generated block-wise randomization list adequate for placebo-controlled studies was prepared by the Programming & Biostatistics Department of [REDACTED]. At each cohort, 6 subjects were randomly assigned to receive cytisine and 2 subjects randomized to receive placebo.

Upon confirmation that all eligibility criteria are met on Day 0, subjects were sequentially assigned a randomization number. The randomization number was provided to the unblinded Pharmacist on site and defined the treatment to which subjects were allocated (test or placebo) per the randomization list.

## 6. STUDY VARIABLES

### 6.1. Safety variables

- Drug exposure
- Adverse events:
  - Reported Term
  - MedDRA SOC coding
  - MedDRA PT coding
  - Start date
  - Start time
  - End date
  - End time
  - Seriousness
  - Severity:
    - Mild
    - Moderate
    - Severe
  - Relationship (causality):
    - not related
    - unlikely
    - possible
    - probable
    - definite
  - Action taken
  - Outcome
- Clinical laboratory evaluations:
  - Biochemistry:
    - aspartate aminotransferase (AST)
    - alanine aminotransferase (ALT)

- gamma-glutamyltransferase (GGT)
- lactate dehydrogenase (LDH)
- alkaline phosphatase (ALP)
- creatine phosphokinase (CPK)
- creatinine
- estimated creatinine clearance (CRCL)
- urea
- sodium
- potassium
- calcium
- glucose
- total cholesterol
- triglycerides
- albumin
- total protein
- uric acid
- direct bilirubin
- indirect bilirubin
- total bilirubin
- Hematology:
  - hemoglobin
  - hematocrit
  - hypochromic red blood cell
  - red blood cell (RBC) count
  - mean corpuscular volume (MCV)
  - mean corpuscular hemoglobin (MCH)
  - mean corpuscular hemoglobin concentration (MCHC)
  - coefficient variation of the red cell distribution width (RDW-CV)
  - total white blood cell (WBC) count
  - neutrophils
  - eosinophils
  - lymphocytes
  - monocytes
  - basophils
  - platelet count
- Coagulation:
  - prothrombin rate
  - prothrombin time - international normalized ratio (INR)
  - activated partial thromboplastin time (aPTT)
- Urinalysis:
  - pH
  - specific gravity
  - protein
  - hemoglobin
  - glucose
  - ketones
  - bilirubin
  - nitrites

- urobilinogen
- microscopy
- Drugs of abuse test:
  - cannabinoids
  - opiates
  - cocaine
  - amphetamines
  - benzodiazepines
- Serum beta-human chorionic gonadotropin (beta-hCG) pregnancy test
- Urine beta-hCG pregnancy test
- Ethanol breath test
- Vital signs:
  - Systolic blood pressure (SBP)
  - Diastolic blood pressure (DBP)
  - Pulse rate
  - Body temperature
- Physical examination
- 12-lead Electrocardiogram (ECG)
- CO

## 6.2. Pharmacodynamic variables

None.

## 6.3. Pharmacokinetic Variables

- Plasma concentrations of cytisine
- Maximum observed plasma concentration post dose, directly obtained from the observed cytisine concentration versus time profile ( $C_{max}$ )
- Time of occurrence of  $C_{max}$  ( $T_{max}$ )

## 7. DATA REVIEW / TRANSFORMATION

### 7.1. Data Management

Data handling will be conducted in accordance with the Clinical Data Management section of the CSP and the Data Management Plan developed by [REDACTED] for this study.

### 7.2. Acceptance of Data

TFLs may start being programmed prior to, or during, the course of the trial. However, the programming of analysis datasets (ADS) and TFLs will only be finished and quality-controlled after database soft lock and unblinding of the data. Only audited cytisine plasma concentration data released by the Bioanalytical Laboratory will be used

for programming the final pharmacokinetic ADS and TFLs.

### 7.3. Data Transformation (CDISC)

Before performing the statistical analysis, all data collected (multiple sources) will be integrated into a common repository, using SAS® 9.4.

For standardization and regulatory submission purposes, all data will be transformed according to Clinical Data Interchange Standards Consortium (CDISC):

- Study Data Tabulation Model (SDTM) version 1.4 or later;
- Study Data Tabulation Model Implementation Guide (SDTMIG) version 3.2 or later;
- The following analysis datasets will be generated (Analysis Data Model [ADaM] version 2.1; Analysis Data Model Implementation Guide [ADaMIG], version 1.1) to support the results and ease the programming activities during the statistical analysis:
  - Subject-Level Analysis Dataset (ADSL)
  - Analysis Data Adverse Events (ADAE)
  - Analysis Data Electrocardiogram (ADEG)
  - Analysis Data Vital Signs (ADVS)
  - Analysis Data Laboratory (ADLB)
  - Analysis Data Pharmacokinetic Concentrations (ADPC)
  - Analysis Data Pharmacokinetic Parameters (ADPP)

## 8. STATISTICAL METHODS

The statistical analysis and TFLs will be done using SAS® for version 9.4.

PK parameters for cytisine ( $C_{max}$  and  $T_{max}$ ) will be estimated using non-compartmental analysis (NCA) in Phoenix® WinNonlin® version 8.1 (Pharsight Corp., Mountain View, CA).

Summaries of demographics, baseline characteristics and safety endpoints will be provided for the Safety Analysis Set, defined as all subjects who received a single dose of cytisine or placebo.

Unless otherwise indicated, numerical variables will be summarized using: number of observations (n), arithmetic mean, standard deviation, coefficient of variation (CV%), median and range (minimum and maximum). Categorical variables will be summarized with number of subjects and percentage within a treatment (dose level). Descriptive statistics will be presented with the same precision as the original data, i.e, the same number of decimals or significant digits.  $T_{max}$  is stated with the same number of significant digits as the actual sampling time. Baseline for post-dose assessments is defined as the last observation recorded before dose. Summaries will be provided for each dose level/treatment (Placebo; 6.0 mg cytisine; 9.0 mg cytisine, etc.). Unless otherwise indicated, no statistical comparisons between the cohorts are planned.

Unscheduled measurements will be listed in the individual data listings. With the

exception of baseline or unscheduled measurements performed due to an error at the scheduled measurement (e.g. equipment failure), unscheduled measurements will be excluded from the descriptive statistical analysis.

No imputation of missing data will be done, except for missing dates and/or times required for the calculation of AEs' time to onset and duration (e.g. see Section 8.7.1) and for plasma concentrations below the lower limit of quantification (LLOQ) (see Section 8.8).

Assessments for trends in dose-limiting adverse events or  $C_{max}$  levels in relationship to BMI categories/levels and baseline Nicotine Metabolite Ratio (NMR) may be explored.

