## **8.3. Demographic and Other Baseline Characteristics**

Subjects demographic data (except date of birth) and other baseline characteristics will be collected at screening and will be listed and summarized descriptively for all subjects by treatment and overall. The data in the summary will include age (years), sex, race, height (cm), weight (kg) and body mass index (BMI,  $\text{kg}/\text{m}^2$ ).

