#### 8.8. Plasma Concentrations

████████████████████ will carry out the determination of plasma levels of cytisine in accordance with the applicable principles of Good Laboratory Practices (GLP), using a previously validated LC-MS/MS analytical method. The pre-planned lower limit of quantification (LLOQ) is 1 ng/mL and the upper limit of quantification (ULOQ) is 400 ng/mL.

Individual (per subject) and mean plasma concentration versus time profiles will be presented for both linear and semi-logarithmic scales. Graphic presentation of individual data will be based on actual blood sampling time, except for pre-dose sampling time which will be assumed as t0.

Descriptive statistics (number of subjects, geometric mean, arithmetic mean, SD, CV%, median, minimum and maximum) of the plasma concentrations will be presented for each time point. Concentrations below the LLOQ will be taken as missing for the calculation of geometric mean and replaced by zero for calculation of the remaining summary statistics.

The pre-dose blood samples were to be collected within 30 minutes prior to dosing. The post-dose blood samples were to be collected within +/-2 minutes from the scheduled sampling time. The clock time was to be recorded and reported for all blood draws and all subjects. A deviation greater than +/-2 minutes will be reported as a protocol deviation and its cause will be recorded.

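### Does the leftover mention of baseline Nicotine Metabolite Ratio in SAP Section 8 leave the plan with an analysis that cannot be done?

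*SAP*

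**What the plan says.** The last paragraph of SAP Section 8 (Statistical Methods) allows an optional look at subject-level factors: trends in dose-limiting adverse events or Cmax "levels in relationship to BMI categories/levels and baseline Nicotine Metabolite Ratio (NMR) may be explored". The abbreviation list in Section 2.2 expands NMR as "Nicotine Metabolite Ratio" and gives no formula, matrix or sampling time.

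The summary of changes from version 1.0 to version 2.0 says that, apart from the three added dose cohorts, the only modification was "removing analysis of cotinine and 3-OH cotinine, as testing will not be conducted, per the Sponsor".

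Section 3.1 states: "There are no changes from the protocol or its amendments".

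The pharmacokinetic variables in Section 6.3 are "Plasma concentrations of cytisine", Cmax and Tmax. Section 8.8 says that the laboratory "will carry out the determination of plasma levels of cytisine" and names no other analyte.

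**The concern.** NMR, as the term is normally used, is the ratio of 3-OH cotinine to cotinine. If neither is assayed, it exists for no subject. Version 2.0 presents the dropped testing as a fact about the current plan, yet the current Section 8 keeps an exploration that needs it. This is therefore not just a change log differing from superseded text.

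Three consequences seem to follow:

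- One of the two factors named for explaining differences in Cmax or dose-limiting events would be empty, leaving BMI alone. The secondary objective in Section 4.2 links Cmax to dose-limiting events, so a reader might think it weakened.
- A reader of the study report could look for an NMR result, find none, and wonder whether it was done and not reported.
- Section 3.1 declares no change from the protocol and does not mention the dropped assay.

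**Working it through.** The SAP gives no figure to reproduce. The check is whether any data could supply NMR, and then whether anything committed depends on it.

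**Is there a data source?** The readable sections were compared in turn.

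| SAP section | Content | NMR or its components? |
|---|---|---|
| 6.1 Safety variables | Adverse events, laboratory tests, vital signs, physical examination, ECG, CO | No |
| 6.3 Pharmacokinetic variables | Cytisine concentrations, Cmax, Tmax | No |
| 7.2 Acceptance of data | Audited cytisine concentrations for the pharmacokinetic datasets | No |
| 8.3 Baseline | "The data in the summary will include age (years), sex, race, height (cm), weight (kg) and body mass index" | No, but BMI is there |
| 8.4 Smoking history | Duration, cigarettes per day, quit attempts, cessation treatments, expired CO | No |
| 8.8 Plasma concentrations | Cytisine assay only | No |
| 9.1 Planned outputs | Listed tables, figures and listings | No |

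The redacted output shells were not used as evidence either way. On the readable text, with NMR in its usual meaning, the NMR part cannot be done and the BMI part can.

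**Does anything committed depend on it?**

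- The wording is permissive. No model, category boundaries, analysis set or output is attached to NMR.
- The same section says: "Unless otherwise indicated, no statistical comparisons between the cohorts are planned". The trend sentence is an option beside the descriptive plan.
- The primary objective (4.1) is met by the adverse event, laboratory, vital sign and ECG presentations in 8.7. None uses NMR.
- The secondary objective (4.2) concerns Cmax and dose-limiting events, and names no covariate.
- The Cmax and Tmax summaries (8.9) are by dose level, and the power model in 8.10 has dose as its only regressor.

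**How many subjects would be involved?** Section 5.2 plans 9 × 8 = 72 subjects. The Pharmacokinetic Analysis Set (8.1.3) holds cytisine recipients only, so at most 9 × 6 = 54 can have a cytisine Cmax. The other 9 × 2 = 18 are on placebo. The figure of 72 could apply only to the adverse-event half of the sentence. Neither count measures an effect on a result, because no planned result uses NMR.

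**The case for a change.** The best case for a change is that permissive wording does not make an impossible analysis possible. The removal announced in the summary of changes was incomplete. This sentence is the only place where the SAP names subject-level factors for Cmax or dose-limiting events. Section 3 requires deviations from the SAP to be justified in the study report, and striking a few words would spare everyone the question.

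The factual part of this stands: the removal was incomplete, and the words could be struck at almost no cost. The rest is weaker.

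- Leaving an optional exploration undone is not a deviation from the plan. The SAP itself says at the front that the testing was dropped and on whose decision, so a reader who asks about NMR has the answer.
- Section 3.1 is wrong only if protocol version 5.0 provides for cotinine or NMR. The summary of changes compares two SAP versions and does not compare the SAP with the protocol. The protocol was not available for this check, so no error in 3.1 can be asserted.
- Other covariates could take the place of NMR, such as body weight, sex, creatinine clearance, cigarettes per day or expired CO. The inconsistency does not call for them. Version 2.0 is dated 17 October 2019, its annex cites blind-review minutes of 10 October 2019, and Section 5.1 describes escalation to 30 mg as complete. Adding five factors at that point, with six cytisine subjects per dose, would widen an exploratory search without a stated reason.

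**Conclusion.** The mention of NMR in Section 8 and in the abbreviation list is a clerical leftover from an assay that the sponsor dropped. An analyst working from this SAP would find no NMR data, explore BMI if anything, and produce every committed table and figure unchanged. The effect on the primary objective, the secondary objective, the Cmax and Tmax summaries and the dose-proportionality estimate is nil. No change to the plan is needed. If the SAP were reissued for another reason, the words could be tidied then.

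This rests on two assumptions. NMR is taken in its usual sense, which the SAP does not spell out. The redacted shells are taken to hold no NMR output beyond the listed titles. If NMR were available from some other source, the apparent inconsistency would disappear. Whether Section 3.1 should mention the dropped testing depends on what protocol version 5.0 provides, and is left open here.
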